6 METHODOLOGY

6.1 Study design

This is a pragmatic, pre- and post-interventional quasi-experimental study combined with a prospective observational study design. The primary aim is to determine the effectiveness of the RITE intervention in increasing the uptake of VMMC at Bwaila STI clinic. The implementation science aim is to determine the potential utility (feasibility, acceptability and appropriateness) of RITE intervention in an STI clinic setting [31]. We will use a sequential mixed methods approach, starting with formative qualitative study to refine the proposed intervention (RITE), followed by a pragmatic, mixed-methods quasi-experimental study with one pre-exposure and four distinct exposure groups [7]. This stand-alone intervention will be implemented at a practical STI clinic setting without random allocation to the intervention. We will observe for the standard of care (SOC) in the pre-intervention phase and introduce our intervention in a step fashion of different intervention combinations with four different intervention groups. This approach will allow us to assess the effect of the intervention while assessing the effect of different combinations of the intervention components, building up to the full intervention. Since the STI clinic is an outpatient clinic and STIs are generally acute infections that resolve quickly with treatment, it is not possible to randomize intervention components and follow the same participants over time as a cohort hence the different exposure groups. The key outcome of interest, VMMC uptake, will be measured at the VMMC facility.

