6.5 Exclusion criteria

Men with prior exposure to research activities who come for repeat STI visits

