Feasibility will be measured during implementation for each implementation block because it cannot be measured before exposure to the intervention [36]. A vignette (embedded in the data tools) on the RITE intervention will be read out to respondents to describe the intervention. Data on acceptability, appropriateness and feasibility will be collected using the following methods:

Surveys: For acceptability, we will use the acceptability of intervention measure (AIM), a tool designed by Weiner et al [37], to collect quantitative data for acceptability. The AIM uses Likert scales of four constructs which assess if an intervention is appealing, likeable, welcome and approved. For appropriateness, we will use the intervention appropriateness measure (IAM) to collect quantitative data for appropriateness [37]. The IAM uses a Likert scales of constructs which assess if an intervention is fitting, suitable, applicable, and a good match. For feasibility, we will used the feasibility of intervention measure (FIM) for feasibility Surveys [37]. The FIM uses a Likert scales of constructs which assess if an intervention is implementable, possible, doable, and easy to use. These tools have been slightly modified to suit the study setting.

Acceptability and appropriateness will be conducted at baseline and for each implementation block except for feasibility which cannot be assessed before exposure to the intervention (Appendix 6 - 9). Surveys data will be collected on electronic tablets through open data kit (ODK). Data clerks will administer surveys on an electronic tablet for the men while HCWs will self-administer the surveys. Each survey will to last approximately 10 - 20 minutes. Survey data will be downloaded from the tablets to a Microsoft Access password-locked database. IDIs and FGDs will complement the surveys.

In-depth interviews: IDIs will be conducted with HCWs from Bwaila STI clinic only. IDIs will

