6.3 Sample Size Calculation and Justification

Data on the incidence of VMMC among men with STIs is unavailable. Based on routine data, the Bwaila STI clinic sees about 60 patients per day. Of these, 27 patients are men. Using the prevalence of circumcision from the MoH integrated HIV Program third quarter report of 28% among men with STI, we estimate that at least 19 uncircumcised men will visit the STI clinic per day and at least 380 uncircumcised men per month. Since the project implementation period is expected to be about 6 months, we expect that a minimum of 2280 uncircumcised men will be exposed to our intervention and observed for VMMC uptake.

We will offer all men who express interest in VMMC to participate in a survey. We anticipate between 5-15% of the men will decline participation in the survey. All (approximately 12) healthcare workers will be offered to take the surveys. All available experts (approximately 10) will be offered to take a survey.

Sample size for surveys

Based on the total sample size of 80 men indicated below, we calculated that 67 surveys are required for each intervention component to achieve 95% confidence level with 5% margin of error [38]. We will offer all men who express interest in VMMC to participate in a survey. We anticipate between 5-15% of the men will decline participation in the survey. All (approximately

12) healthcare workers will be offered to take the surveys. All available experts (approximately 10) will be offered to take a survey.

Data Analysis

Overall, we will use descriptive statistics such as mean, median and proportion to describe the demographic characteristics of the study population by implementation block. Demographic characteristics will include but not limited to age, marital status, educational status and socio-economic status. These characteristics will be compared with the SOC group using Student's T-test or Chi-squared test at $\alpha=0.05$ and 95% confidence interval, assuming normal distribution.

Objective 1: To compare uptake of voluntary medical male circumcision between the standard of care and the different combinations of the RITE intervention among men attending Bwaila STI clinic in Lilongwe Malawi

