Uptake will be calculated as a proportion - the number of men who will undergo VMMC divided by the number of uncircumcised men offered VMMC at the STI clinic. Uptake will be calculated for each implementation block. Uptake for each block will be compared against SOC using Student's T-test at $\alpha=0.05$ significance level and 95% confidence interval, assuming normal distribution.

Objective 1a: To compare time-to-uptake of voluntary medical male circumcision between the standard of care and intervention period among men attending Bwaila STI clinic in Lilongwe Malawi

Time-to-uptake of VMMC will be calculated as the number of days taken for an individual to undergo circumcision at the VMMC clinic from the day they were offered circumcision at the STI clinic. To compare time-to-uptake between SOC and the intervention blocks, we will conduct time-to-event analysis to estimate duration to circumcision and Kaplan Meier curves will be plotted and compared between SOC and implementation blocks. We will also study factors affecting time-to-uptake using cox regression.

Objective 1b: To assess factors affecting uptake of voluntary medical male circumcision among men attending Bwaila STI clinic in Lilongwe Malawi

We will assess factors affecting uptake of VMMC using logistic regression modeling. We will use univariate models to assess association. Covariates with $P<0.05$ and those based on expert knowledge of this topic will be fit into multivariate logistic regression models to control for confounders.

Objective 2: To develop STI clinic setting-specific voluntary medical male circumcision educational material at Bwaila STI clinic in Lilongwe Malawi

We will use thematic analysis approach for qualitative analysis of the consultative meeting notes. The notes will be coded and salient themes will be identified. The content and delivery methods will be deduced from the salient themes.

Objective 3: To assess the acceptability, appropriateness and feasibility of the adaptable RITE intervention among men and healthcare workers at Bwaila STI clinic in Lilongwe, Malawi.

We will use mixed methods to assess acceptability, appropriateness and feasibility. For acceptability, appropriateness and feasibility quantitative surveys, these outcomes will be

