calculated as a median score and percentages for each of the survey questions. The results will be compared between SOC and each implementation block using Wilcoxon sign-ranked test, analysis of variance (ANOVA) and test of proportions as required. We propose to use structural equation modelling to assess predictors of acceptability, appropriateness and feasibility. The latent variables will be acceptability, appropriateness and feasibility. We assume that the constructs measuring each of these latent variables are correlated, we will conduct principal component analysis and calculate factor loadings and error variance to estimate the true effect of the constructs. We also assume that the latent variables will be correlated. Therefore, we will conduct confirmatory factor analysis to assess how the latent variables will affect the impact of our intervention on uptake of VMMC.

Qualitative data will be analyzed using a thematic approach (thematic framing and coding, indexing, and charting). We will conduct data analysis concurrent with interviews to identify salient themes and areas that may require further exploration in the subsequent interviews. Salient themes will be deduced from codes identified from the IDIs and FGDs.

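### Objective 3 surveys: the only rank test named is a paired one, feasibility has no standard-of-care value to be compared with, and two sections recruit survey respondents by different rules (minor)

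*Combined protocol and SAP*

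**What the plan says.** **Analysis (section 6.3, Data Analysis, Objective 3).** The sentence on the surveys begins "For acceptability, appropriateness and feasibility quantitative surveys, these outcomes will be" and continues "calculated as a median score and percentages for each of the survey questions". The results are then to be "compared between SOC and each implementation block using Wilcoxon sign-ranked test, analysis of variance (ANOVA) and test of proportions as required". Men and healthcare workers are treated together, and the text does not say which test goes with which respondents.

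**Who the men are.** Section 6.1 (Study design) explains that it is not possible to "follow the same participants over time as a cohort hence the different exposure groups". The one exclusion in section 6.5 is "Men with prior exposure to research activities who come for repeat STI visits".

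**When feasibility is measured (section 6.2, Data Collection, Objective 3).** The plan states: "Feasibility will be measured during implementation for each implementation block because it cannot be measured before exposure to the intervention". The paragraph on surveys says it again: acceptability and appropriateness are surveyed at baseline and "for each implementation block except for feasibility which cannot be assessed before exposure to the intervention".

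**Who is surveyed.** The Sampling section (the second section numbered 6.1) has men in both the surveys and the focus groups recruited purposively and segmented by characteristics such as age or religion. It also selects healthcare workers purposively for interviews and surveys. The sample size section (6.3) says instead: "We will offer all men who express interest in VMMC to participate in a survey". It also offers the surveys to all healthcare workers, approximately 12. Objective 3a in section 5.4.2 speaks of men at the clinic.

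**The concern.** The signed-rank test works on within-pair differences. It fits one respondent measured twice, or a genuine matched pair. The men have neither, because each is surveyed in one period only. An analyst who reports medians and looks in the plan for the matching rank test will find only the paired one. Using it on the men means inventing pairs.

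Two further problems affect the same analysis. One listed contrast, feasibility in a block against feasibility under SOC, has no SOC measurement behind it. And the population that the survey scores describe is not settled: purposively chosen men and all interested men are different groups. Interest in circumcision is something the intervention tries to change, so under the second rule the type of man surveyed could shift between periods.

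At stake is the clarity of the Objective 3 results, which are also a planned publication.

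**Working it through.** **1. Match the test to the data.** For pairs (x_i, y_i), signed-rank ranks |x_i − y_i| and sums the signed ranks, so the result depends on who is paired with whom. Rank-sum compares every man in one group with every man in the other and uses no pairing.

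| Respondents | Same people across periods? | Rank test that fits |
|---|---|---|
| Men | No (Study design, Exclusion criteria) | Rank-sum |
| Healthcare workers | Possibly, as about 12 are offered the surveys | Signed-rank, if responses are linked |

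**2. Reproduce the survey size.** Inputs from section 6.3: 80 men, 95% confidence, 5% margin, 67 surveys per component. A proportion of 0.5 is assumed, since none is stated.

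- n0 = 1.96² × 0.25 / 0.05² = 384.15 (unrounded z)
- n = 384.15 / (1 + 383.15/80) = 66.35, rounded up to 67. The plan's figure reproduces.
- With 5–15% declining: 80 × 0.95 = 76 and 80 × 0.85 = 68.

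The sizes used below are therefore 67 v 67 and 68 v 76. In the second case, pairing drops 76 − 68 = 8 men.

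**3. Cost of using signed-rank on the men.** The documents give no score distribution, so these probabilities for scores 1 to 5 are assumptions:

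- SOC: .05, .10, .20, .40, .25
- Moderate effect: .03, .07, .15, .40, .35
- Larger effect: .02, .05, .13, .38, .42

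Each cell has 8,000 simulated data sets, tested two-sided at 0.05. Signed-rank used arbitrary pairs; rank-sum used all men.

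| Scenario | Sizes | Signed-rank | Rank-sum | Difference (points) |
|---|---|---|---|---|
| No effect | 67 v 67 | 4.8% | 4.7% | – |
| No effect | 68 v 76 | 5.0% | 4.9% | – |
| Moderate | 67 v 67 | 30.5% | 32.5% | 2.0 |
| Moderate | 68 v 76 | 30.2% | 34.9% | 4.7 |
| Larger | 67 v 67 | 65.4% | 68.3% | 2.9 |
| Larger | 68 v 76 | 67.3% | 72.3% | 5.0 |

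A separate run of 3,000 per cell gave differences of 1.4, 3.3, 2.5 and 5.7 points in the same order. The standard error of one power figure near 68% in that run is √(0.68 × 0.32/3000) = 0.85 points, so the two runs agree.

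**4. Dependence on the pairing.** With 67 men per group, 300 data sets were each re-paired 100 times. The mean share of pairings on the minority side of p = 0.05 was 1.6% (no effect), 4.4% (moderate) and 4.6% (larger). In one further data set, 5,000 re-pairings moved the signed-rank p-value between 0.38 and 0.90; rank-sum gave a single value, 0.81.

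**5. ANOVA, which the plan already names.** In another run of 3,000 per cell, power for ANOVA v rank-sum was:

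- 67 v 67: 30.9% v 32.5% (moderate) and 68.8% v 69.3% (larger)
- 68 v 76: 32.6% v 33.9% (moderate) and 71.2% v 72.4% (larger)

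ANOVA stays within 2 points of rank-sum.

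**6. Which contrasts have data.** The baseline survey is taken to supply the SOC value.

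| Outcome | Baseline / SOC | Each block | Block v SOC possible? |
|---|---|---|---|
| Acceptability | Yes | Yes | Yes |
| Appropriateness | Yes | Yes | Yes |
| Feasibility | No | Yes | No; between blocks only |

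**7. Recruitment rules side by side.**

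| Respondents | Sampling section | Sample size section |
|---|---|---|
| Men, surveys | Purposive, segmented | All who express interest in circumcision |
| Healthcare workers, surveys | Purposive | All, approximately 12 |

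**The case against.** The plan lists its tests to be used as required and never assigns signed-rank to the men. ANOVA and the test of proportions both suit independent groups, and step 5 shows that ANOVA does nearly the same job as rank-sum. This stands, and it is why the point is minor. What remains is that the scores are reported as medians, ANOVA compares means, and the one rank test offered is the wrong one for the men.

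The methods summary in Appendix 12 and the survey forms in Appendices 6–9 are not in the text available. They might assign tests to respondents or carry a linking code. They would not remove the two conflicts in the body text.

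On feasibility, a careful analyst would see that no SOC value exists and compare blocks only, so no wrong result would follow. That is fair; the sentence still promises a contrast that cannot be run.

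On recruitment, the section on focus groups repeats the segmentation wording for focus groups only, so the Sampling section may simply have merged two activities. That is plausible for the men. It does not explain the separate conflict for healthcare workers.

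A reader might infer stronger claims that the documents do not support:

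- **No valid test is named for the men.** Two are; only the rank test is missing.
- **Signed-rank is wrong throughout.** It can suit linked healthcare-worker responses.
- **The false-positive rate is raised.** Step 3 shows that it is not.
- **The loss is larger, from setting 67 against 80 men.** That needs no refusals in one group, whereas the plan expects 5–15%.
- **The survey results are biased in a known direction.** Nothing in the documents gives a size or a direction.

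**Conclusion.** The point holds as a minor one. Three pieces of text need correcting: the rank test for the men, the feasibility comparison with SOC, and the survey recruitment rules for both respondent groups. All three follow from reading the sections against each other and do not depend on the simulation.

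If signed-rank were used for the men, the cost would be about 1 to 5 points of power (5.7 in one cell of the shorter run), up to 8 men dropped, and a p-value tied to an arbitrary pairing. Those sizes rest on the assumed Likert distributions and on the plan's figures of 67, 80 and 5–15%. They support no more than the word small. The effect of the recruitment conflict cannot be sized from the documents; until it is settled, it is unclear whether Objective 3a describes clinic men or only men interested in circumcision.

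A reader might infer that the main result is in doubt. It is not: uptake is measured and analysed separately, and percentage comparisons and feasibility between blocks stand.

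**What to change.** In Data Analysis, Objective 3, replace the sentence on comparisons with wording such as:

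> Men: acceptability and appropriateness scores in each block will be compared with SOC by the Wilcoxon rank-sum test, and percentages by a test of proportions. Healthcare workers: the signed-rank test will be used only for responses linked across periods by a non-identifying code, and the number of linked pairs will be reported. Feasibility will be compared between implementation blocks only.

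Whether to keep ANOVA as well, and how to handle healthcare-worker responses that cannot be linked, are choices for the investigator. The plan should state them. Add a linking code to the healthcare-worker survey if the forms do not already carry one; this is compatible with the commitment in section 6.4 to hold no identifiable data.

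Reconcile the Sampling section with the sample size section into one survey recruitment rule for men and one for healthcare workers, each applied in SOC and in every block. If segmentation was meant for focus groups only, remove the surveys from that sentence. If the rule of offering the survey to interested men is kept, limit the Objective 3a conclusion to men interested in circumcision.

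The cost is a few sentences and possibly one survey field. The sample size of 67 does not change.

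### The question of how acceptability, appropriateness and feasibility affect the impact on uptake is assigned to confirmatory factor analysis, which cannot estimate it, and error variance is assigned to principal components, which have none

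*Combined protocol and SAP*

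**What the plan says.** Section 6.3, Data Analysis, Objective 3, first describes medians, percentages and block comparisons for the survey questions. It then adds a latent-variable analysis that names three techniques.

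- **SEM:** "We propose to use structural equation modelling to assess predictors of acceptability, appropriateness and feasibility". The next sentence reads "The latent variables will be acceptability, appropriateness and feasibility".
- **PCA:** "we will conduct principal component analysis and calculate factor loadings and error variance to estimate the true effect of the constructs".
- **CFA:** the plan says "We also assume that the latent variables will be correlated" and, for that reason, "we will conduct confirmatory factor analysis to assess how the latent variables will affect the impact of our intervention on uptake of VMMC".

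The indicators are described in section 6.2, Objective 3, Surveys. For acceptability: "The AIM uses Likert scales of four constructs which assess if an intervention is appealing, likeable, welcome and approved". The appropriateness scale is listed as "fitting, suitable, applicable, and a good match", and the feasibility scale has four further descriptors. The same section says that the tools were modified slightly for the setting and that feasibility is not measured before exposure.

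Uptake is handled separately. Objective 1 compares the proportion circumcised in each block with standard of care by t-test. Objective 1b uses logistic regression, and section 6.2 lists its covariates as demographic, sexual-history and HIV/ART data.

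**The concern.** Two of the three techniques are asked for quantities that they do not contain.

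A CFA describes how survey items reflect the latent variables and how those variables correlate. It has no path from a latent variable to an outside event such as circumcision, and no term for implementation block. The plan nevertheless gives it the question that joins the survey work to the effectiveness result.

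PCA splits the total variance of the items into components and does not separate true score from measurement error. What is left over depends on how many components the analyst keeps, so it cannot serve to correct an effect for measurement error, which seems to be the plan's purpose.

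An analyst who followed the text would finish with factor loadings and fit statistics, but with no estimate of whether the effect on uptake depends on, or passes through, how men viewed the intervention.

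**Working it through.** The plan gives no figure for this analysis, so there is none to reproduce. The check compares what each method estimates with what it is asked to deliver. The documents give no loading, latent correlation or effect size, so all such values below are assumptions. Four items per scale is stated for the acceptability measure and inferred for the other two from the four descriptors listed for each. The survey forms (Appendices 6 to 9) are not in the available text.

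**1. CFA and uptake**

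- Twelve items supply 12 × 13 / 2 = 78 variances and covariances.
- Three correlated factors with unit variance need 12 loadings + 12 error variances + 3 latent covariances = 27 parameters, leaving 78 − 27 = 51 degrees of freedom.
- None of the 27 refers to uptake or block.

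A simulation shows the consequence. One set of item responses was generated for 400,000 men (loading 0.70, latent correlation 0.6). Uptake was then generated twice from a logistic model with intercept −1.5.

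| Log-odds effect of acceptability on uptake | Uptake | Correlation of one acceptability item with uptake | Item correlations within / between scales |
|---|---|---|---|
| 0 | 18.3% | 0.000 | 0.489 / 0.292 |
| 1.0 | 22.1% | 0.251 | 0.489 / 0.292 |

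The last column is all that the CFA sees. It is the same in both rows, so the CFA cannot tell no effect from a strong one.

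**2. Is the missing model elsewhere?**

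- SEM in the same paragraph: the latent variables are the outcomes, and uptake is not mentioned.
- Objective 1: t-tests of uptake by block, with no survey score.
- Objective 1a: Kaplan-Meier curves and Cox regression, with no survey score named.
- Objective 1b: logistic regression on clinic-registry covariates, with no survey score.

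No text gives a path, mediation term or interaction term that joins block, latent variable and uptake.

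**3. PCA and error variance**

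Assume loading λ = 0.70 and latent correlation φ = 0.6. The true error variance is 1 − 0.49 = 0.51. Items correlate 0.49 within a scale and 0.6 × 0.49 = 0.294 between scales. The eigenvalues of the 12-item matrix are:

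- first: 1 + 3(0.49) + 8(0.294) = 4.822
- second and third: 1 + 3(0.49) − 4(0.294) = 1.294 each
- the other nine: 1 − 0.49 = 0.51 each

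The items are symmetric, so each has residual 1 − (sum of kept eigenvalues) / 12.

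| Components kept | Calculation | PCA residual | True error variance |
|---|---|---|---|
| 1 | 1 − 4.822/12 | 0.598 | 0.51 |
| 3 | 1 − 7.410/12 | 0.383 | 0.51 |
| 12 | 1 − 12/12 | 0 | 0.51 |

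With one component the loading is √(4.822/12) = 0.634, below the true 0.70.

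If PCA is instead run on each four-item scale with one component kept, the eigenvalue is 1 + 3(0.49) = 2.47. The loading is √(2.47/4) = 0.786 and the residual 1 − 0.6175 = 0.383. In general that residual is 1 − (1 + 3λ²)/4 = 3(1 − λ²)/4, always three quarters of the true value: 0.5625 against 0.75 at λ = 0.5, and 0.1425 against 0.19 at λ = 0.9.

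One component over 12 items overstates error whenever (1 + 3λ² + 8φλ²)/12 < λ², that is φ < (9λ² − 1)/(8λ²). At λ = 0.70 this is 3.41/3.92 = 0.87. The direction therefore depends on a choice that the plan does not state and on a correlation not yet known.

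**The case against.** The best defence is that the paragraph is loosely worded, not wrong. It opens with SEM and then lists latent variables, loadings, error variances and CFA, which are the usual parts of an SEM. Some software also labels PCA output as factor loadings. The planned CFA would itself give proper loadings and error variances, so these tasks are partly misassigned rather than impossible. All of this stands, and it weakens the PCA part. It does not supply the missing uptake path: SEM is limited in the text to predictors of the latent variables, and the uptake question is given to CFA by name.

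A reader might infer that PCA will inflate the loadings and understate the error. The documents do not support that. It holds for one component per four-item scale. One component over all 12 items reverses it at the assumed values, and the plan states neither arrangement.

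A reader might also infer that surveys and uptake cannot be linked. Section 6.2 puts survey data in Microsoft Access and uptake data in Excel, and section 6.4 says that stored data will not identify participants. The available text mentions no linking code. The forms are not available, however, so whether one exists cannot be judged.

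It is also fair to say that the effect of the latent variables on uptake is not among the specific objectives in section 5.4.2. That limits the weight of the point.

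**Conclusion.** The point holds for one stated analysis within Objective 3. As written, the plan would give no estimate of how acceptability, appropriateness and feasibility bear on the intervention's effect on uptake, because the method named has no parameter for uptake or block and no other section supplies one. This follows from the structure of the method and rests on no assumed number.

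The PCA part is secondary. PCA gives no measurement-error variance, and its residual can lie above or below the true value. The range of 0 to 0.598 against 0.51 rests on an assumed loading of 0.70, an assumed latent correlation of 0.6 and an inferred four items per scale.

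A reader should not conclude that the effectiveness result is at risk. The primary uptake comparison does not use these models. The medians, percentages and block comparisons of survey scores do not depend on them either.

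**What to change.** Rewrite the latent-variable text under Objective 3 as follows.

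1. Take loadings and error variances from the CFA measurement model, with an estimator suited to ordinal Likert items. Do not take them from PCA.
2. Extend the planned SEM with a structural part. The outcome is individual circumcision (yes/no), and the predictors are block, the latent variable and a block-by-latent term. That term answers the question as worded, which reads as effect modification. If mediation is meant, say so and specify block-to-latent and latent-to-uptake paths instead.
3. Use men's surveys only. Leave the roughly 12 healthcare workers and 10 experts in section 6.3 out of this model.
4. Link each survey to the uptake record by a coded study number.
5. Restrict feasibility to comparisons among the intervention blocks, because it has no pre-exposure measurement.
6. Label the analysis exploratory.

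The cost is a revised paragraph and, if none exists already, a linking code on the survey and uptake forms. Whether the code needs further ethics review cannot be judged from the available text. It should be settled before data collection, since unlinked records may not be joinable later. Two limits should be stated. Precision will be modest at the planned 67 surveys per intervention component, above all for interaction terms. The results will apply only to men who expressed interest in circumcision, since section 6.3 offers the survey to that group.
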